Participants will be provided hardware including 3-sensor inertial system and lumbar sensor with detailed written and video instructions. Participants will also be provided with cones connected with a string that is 7-meters long for the gait test, a chair for the sit-to-stand tests, and a step-up box for the step-up tests. A tele-research visit will be scheduled during which the researchers will guide the participants through application of all sensors and the tests. Physical performance tests will include 7-meter gait test, 5 times sit to stand test (collected as part of the modified short-performance physical battery), and 15 second step-up test. All of these tests will be done with the lumbar sensor, 3-sensor inertial system, and wrist sensor worn by the participant. After the tests are complete the participants will be asked to remove all sensors and wait for 15-minutes during which time they may be asked to complete questionnaires described elsewhere. After 15-minutes, the participants will re-place all of the sensors and repeat all the activities. At the end of the tele-research visit, participants will be guided into removing the sensors and mail it back to the research team. The lumbar sensor may be kept on depending on whether the participants have already completed the in-person visit or not.

In-lab visit:

This is the same as the baseline visit in the parent study.

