4. STUDY DESIGN

4.1. Overall Study Design

Participants with baseline pain during weight-bearing activities due to their knee OA will be recruited to a 19-week study. Eligible participants will be assessed at baseline and will undergo a supervised exercise-based PT program for 12 weeks as well as multiple in-lab functional assessments of strength, balance, pain, and gait while being monitored with an optical motion capture system, inertial motion capture system, surface EMG, and two wearable sensors at the wrist and lumbar areas (Actigraph and Axivity, respectively). Additional study visits will occur at week 6 and week 12 (end of PT). Participants' activities will be continuously monitored in the real world with the wrist sensor for the total duration of the study and for week-long periods with the lumbar sensor. There will be an additional 6-week monitoring period to measure persistence of treatment effect (i.e., week 12 to 18). The final in-lab visit will occur at the end of 18-weeks and the final at-home assessment with the lumbar and wrist sensors will occur in week 19. In case, in-lab visits are not possible due to COVID-19, a modified protocol will be used to collect outcomes remotely.

4.2.

Sample Size Calculation

The sample size calculation for this study was based on the traditional primary outcome for OA studies, i.e. the WOMAC pain and function scores. A successful digital endpoint can detect changes with treatment with a smaller sample size than the WOMAC. Meta-analyses of published RCTs on land-based therapeutic exercise compared with a non-exercise control report (Fransen et al, 2015) an effect size of 0.49 (95%CI 0.39-0.59) for improvements in pain immediately post-treatment and an effect size of 0.52 (95%CI 0.39-0.64) for improvements in function immediately post-treatment. To account for potential differences in study populations and intervention protocols, we used conservative effect sizes of 0.40 for both pain and function outcomes. Given this effect size, assuming a significance level of 0.05 with a two-tailed distribution and power of 80%, the total sample size estimated for a paired t-test analysis is 52 for a single-arm study. Accounting for an expected 10% attrition, we would need 57 participants. Hence, the proposed sample size of 60 should be sufficient to detect significant changes in the WOMAC scores (traditional primary outcomes).

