2. Examine agreement between wearable sensor data collected during in-lab and at-home physical performance tests

Participants will be wearing a 3-sensor inertial system in addition to the lumbar sensor.

Recruitment and screening: Participants from the parent study who are able to attend a baseline visit in-lab will be asked to participate in the substudy, for up to a total sample size of 20.

Substudy sample size: The size of the substudy was based on data collected from a group of healthy adults (n=32, [65-85] years old). Test-retest reliability of gait metrics between two lab visits derived from lumbar sensor data using the GaitPy algorithm (Czech et al., 2019) and calculated using the intraclass correlation coefficient (ICC) was 0.85 [0.71 0.92] for gait speed. To be able to replicate these substantial ICC values between two at-home assessments, we estimate that we need at least 11 participants (based on ICC H_0 of 0.42 computed by generating a null distribution based on 10,000 permutations of the gait speed across subjects between visit 1 and visit 2 and taking the 99th percentile of this distribution as ICC H_0 ; an ICC of 0.85, and using a one-tailed test with alpha=0.05 and power=0.8; Computed using R package ICC.Sample.Size; Zou, 2012).

Considering 10% attrition, we estimate that 12 participants are required for this substudy.

We will undertake interim analysis after 12 participants have completed the substudy (while continuing to enroll) to determine if additional participants are required to address the aims of this substudy.

Assessments: Participants will be asked to participate in 2 assessments of which 1 will be in-lab and 1 will be at-home. The order of these assessments will be randomized and occur within 2-weeks of each other.

At-home Visit

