#### **4.5. Analysis of Substudy Endpoint(s)**

*Substudy Aim 1: Examine the test-retest reliability of at-home instrumented physical performance tests*

Test retest reliability of sensor metrics derived during the two sets of at-home physical performance tests (7-meter gait task, 5 times sit to stand tasks) will be assessed using ICC and correlation analyses. Pearson's product-moment correlations or Spearman's rank order correlations will be used depending on their normality. These analyses will be conducted on all sensor metrics derived from the 3-sensor IMU system and GaitPy and Sit2StandPy applied to the lumbar sensor (Tables 3. and 4.).

*Substudy Aim 2: Examine agreement between wearable sensor data collected during in-lab and at-home instrumented physical performance tests*

We will assess agreement between wearable sensor metrics collected in-lab and those collected at-home during the same physical performance tests (7-meter gait, 5 times sit to stand) from the 3-sensor IMU system and the lumbar sensor separately. Agreement will be assessed using ICC analyses as well as Bland–Altman plots and 95% limits of agreement between at-home and in-clinic sensor metrics for both systems (using metrics listed in Tables 3. and 4.).

As stated in the protocol, these analyses will be performed on a subset of participants (n=12). Once 12 participants have had the opportunity to complete the study, an interim analysis may be conducted (while continuing to enroll) to determine if additional participants are required to address the aims of this substudy.

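### SAP 4.5 lets withdrawn participants count towards the 12 that trigger the substudy interim, whereas the protocol requires 12 completers; separately, the attrition-adjusted sizes 12 and 57 are each one short

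*Protocol*

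**What the plan says.** **Interim trigger.** Protocol 6a (Substudy) says: "We will undertake interim analysis after 12 participants have completed the substudy (while continuing to enroll". SAP 4.5 says: "Once 12 participants have had the opportunity to complete the study, an interim analysis may be conducted (while continuing to enroll". Both give the same purpose, which is to decide whether the substudy needs more participants. Just before its trigger, SAP 4.5 gives the analysis size as n=12 and attributes that figure to the protocol.

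**Substudy size.** Protocol 6a concludes that "we estimate that we need at least 11 participants", then adds: "Considering 10% attrition, we estimate that 12 participants are required for this substudy". Recruitment may go up to 20.

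**Main study size.** Protocol 4.2 needs 52 for a paired t-test and continues: "Accounting for an expected 10% attrition, we would need 57 participants". It proposes to enrol 60.

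**Precedence.** Protocol 7.1 says that the approved SAP is followed where its analyses differ from the protocol's. SAP section 1 says that the SAP may modify the protocol's plans.

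**The concern.** The two trigger sentences would start the interim at different moments and on different people. Under the protocol, a participant counts only after finishing the substudy. Under the SAP, a participant counts once the chance to finish has passed, so someone who withdrew still counts. The SAP text does not present this as a change, and its n=12 sentence points back to the protocol as if the two agreed. By the precedence rule, the looser wording probably governs.

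At stake is the basis of one decision, whether to keep adding participants. That look could be taken on fewer evaluable people than the plan's own minimum of 11.

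The attrition figures raise a related but separate point. A stated minimum with an allowance for loss should still be met, on average, after the loss. Neither 12 nor 57 does this.

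**Working it through.** **1. The base sizes reproduce.**

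- *Substudy.* Inputs from Protocol 6a: a null ICC ("based on ICC H_0 of 0.42 computed by generating a null distribution") and "an ICC of 0.85, and using a one-tailed test with alpha=0.05 and power=0.8". Two at-home test sets give k = 2 measurements per person. Formula: n = 1 + 2k(z₀.₉₅ + z₀.₈₀)² / [(k − 1)(ln C)²], where C = [1 + kρ₀/(1 − ρ₀)] / [1 + kρ₁/(1 − ρ₁)]. Here C = 2.448/12.333 = 0.1985 and ln C = −1.617. So n = 1 + 4 × 6.183/2.614 = 10.46, rounded up to **11**, as stated. Exact F-test power is 0.810 at 11 and 0.773 at 10.
- *Main study.* Inputs from Protocol 4.2: standardised effect 0.40, two-sided 0.05, power 80%. The exact paired t-test needs **52** (power 0.808), as stated. Power at 51 is 0.7999.

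**2. The attrition step.** With 10% of those enrolled lost, the enrolled number is the needed number divided by 0.9, rounded up.

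| | Needed | Stated | Stated × 0.9 | Needed/0.9 | Rounded up |
|---|---|---|---|---|---|
| Substudy | 11 | 12 | 10.8 | 12.22 | 13 |
| Main study | 52 | 57 | 51.3 | 57.78 | 58 |

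Each stated size is one participant short. The replacements hold on average: 13 × 0.9 = 11.7 and 58 × 0.9 = 52.2.

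**3. The triggers side by side.**

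| | Protocol 6a | SAP 4.5 |
|---|---|---|
| Who counts towards 12 | Those who completed | Those who had the chance to complete |
| Complete what | The substudy | The study |
| Obligation | Will | May |

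**4. What the SAP trigger can deliver.** If exactly 12 are counted and each is lost independently with probability 0.10, the chance of at least 11 completers is 0.9¹² + 12 × 0.1 × 0.9¹¹ = 0.282 + 0.377 = 0.659. The chance of fewer than 11 is therefore **0.34**. Under the protocol trigger, 12 completers are present by definition, although the protocol does not say that their sensor data must be usable.

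**5. What enrolment already covers.** The main study's 60 leaves 54 expected completers, and at least 52 with probability 0.86 (from 57 it would be 0.49). The substudy's 20 leaves 18 expected, and at least 11 with probability above 0.999.

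**The case against.** The strongest reply is that little follows from either point. The interim is there to ask whether more people are needed, enrolment continues meanwhile, and neither document attaches a stopping or success rule to it. A look at 10 people instead of 11 lowers power from 0.810 to 0.773 and can be followed by further enrolment up to 20. The figures 12 and 57 are not enrolment ceilings. All of this stands and keeps the point minor. It does not reconcile the two triggers or make the stated sizes meet their own minima.

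Four stronger readings are tempting, and the documents do not support them:

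- *The attrition was applied with the wrong formula (multiplying by 1.1).* The method is not stated. For the substudy, 11/0.9 = 12.22 and 11 × 1.1 = 12.1 both round to 12. For the main study, 57 fits 52 × 1.1 = 57.2 rounded, but also 57.78 truncated. Even the 1.1 method gives 13 and 58 if rounded up. Only the failure to round up far enough can be shown.
- *The substudy has a 34% risk of ending too small.* That probability belongs to a look taken on exactly 12 counted people with no replacement. It is not the risk for the completed substudy, which may enrol 20.
- *The main study is underpowered through attrition.* It enrols 60, so only the printed 57 is affected.
- *The SAP delays the look until 12 people finish the whole 19-week study.* The word used is *study*, but the sentence sits in the substudy section and ends by naming the substudy. The intended meaning cannot be settled from the text.

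**Conclusion.** The conflict between SAP 4.5 and Protocol 6a is real, and by Protocol 7.1 the SAP wording can govern. Read that way, withdrawals count towards the 12, and the look that decides on further enrolment falls below the plan's minimum of 11 with probability 0.34. This assumes that exactly 12 are counted, that loss is 10% and independent between participants, and that the precedence rule for analyses extends to the interim trigger.

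The attrition point is a separate, one-participant shortfall in each stated size, reading attrition as a 10% loss of those enrolled. It has no practical effect on the main study and, given the cap of 20, little on the substudy.

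This is an inconsistency with a minor arithmetic correction: worth fixing because it touches a decision rule and two stated sample sizes, but not a threat to the trial's conclusions.

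**What to change.** 1. SAP 4.5: run the interim once 12 participants have completed the substudy. Define completion as both at-home test sets and the in-lab visit, with usable sensor data. Make up losses within the permitted 20.
2. Both documents: use the same completion definition, settle whether the interim will or may be done, and refer to the substudy throughout.
3. SAP 4.5: reword the n=12 sentence as 12 completers, so that it does not clash with an enrolment figure of 13.
4. Protocol 6a: restate 12 as 13. Protocol 4.2: restate 57 as 58. Make clear that 13 is the planning figure for 11 evaluable participants and is distinct from the 12-completer trigger.

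**Cost.** These are text edits, with no enrolment beyond the planned 60 and 20. Reaching 12 completers at 10% loss takes about 12/0.9 = 13.3 enrolled, so the interim may come one or two participants later, or slightly more if sensor data are lost.

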6.1 Activities/Assessments and Associated Endpoints

6.1.1 In-Lab Gait, Strength, and Functional Assessments

3D Motion Capture Assessment

Participants will perform specific tasks while being monitored with a 3D motion capture system, wrist and lumbar wearable sensors, and surface electromyography (EMG) sensors. For 3D tracking, small plastic lightweight markers will be placed (14 mm in diameter) on the legs and trunk. These markers are covered in retro-reflective tape and can be detected by the optical motion capture cameras. Surface electromyography (EMG) sensors will be placed on vastus lateralis, vastus medialis, medial hamstrings, lateral hamstrings, medial gastrocnemius, and lateral gastrocnemius muscles after cleaning and shaving the skin. The tasks to be performed include (a) walking at self-selected speed (4-12 trials), (b) walking at fast speed (4-12 trials), (c) sit to stand (4 trials), and (d) standing with eyes open and eyes closed (two 30 second trials in each condition). Practice trials are performed prior to each task.

Devices to be used: Qualisys cameras, Sony video camera, AMTI force plate, AMTI staircase, Delsys EMG

Raw Data obtained:

- Ground reaction force (x, y, z)
- Marker trajectories (x, y, z)
- Raw electromyogram (various muscles – VM, VL, MH, LH, MG, LG)

Derived measures:

Gait Measures
Cadence (steps/min)
Step length symmetry
Gait speed (m/s)
Stride duration (s)
Stride duration asymmetry (s)
Step duration (s)
Step duration asymmetry (s)
Initial double support time (s)
Terminal double support time(s)
Total double support time (s)
Single limb support time (s)
Stance time (s)
Swing time (s)
Step length (m)
Peak knee index (%BodyWeight x Height)
Knee flexion excursion (deg)
Knee extension excursion (deg)
Peak medial quadriceps-medial hamstrings co-contraction during loading response during walking at self-selected pace
Peak lateral quadriceps-lateral hamstrings co-contraction during loading response during walking at self-selected pace
Peak sagittal trunk angle (deg)
Peak knee adduction moment (%BodyWeight x Height)
Peak knee flexion moment (%BodyWeight x Height)
Knee adduction moment impulse (%BodyWeight x Height x Sec)
Knee flexion moment impulse (%BodyWeight x Height x Sec)
Peak sagittal total support moment (%BodyWeight x Height)
Sit-to-stand measures

Number of sit-to-stands
Duration (s)
Maximum acceleration (m/s ²)
Minimum acceleration (m/s ²)
Peak total sagittal lower extremity support moment (%Bodyweight*Height)
Peak sagittal trunk angle (deg)
Peak medial quadriceps-medial hamstrings co-contraction
Peak knee adduction moment (%BodyWeight x Height)
Peak knee flexion moment (%BodyWeight x Height)
Peak knee flexion (deg)
Balance Measures
Center of pressure displacement in A-P direction (mm)
Center of pressure displacement in M-L direction (mm)
Mean center of pressure velocity (mm/s)

Strength Assessment

Participants' strength will be evaluated with an isokinetic dynamometer through tasks of knee flexion and extension on the side of the index joint. Tests include maximal isometric extension torque (x3), maximal isometric flexion torque (x3), isokinetic flexion-extension at 60 deg/s (x2), and isokinetic flexion-extension at 120 deg/s (x2). Additionally, isometric plantarflexion trials (x2) will be recorded for the purpose of EMG normalization.

Device to be used: Biodex System 3

Raw Data obtained:

- Torque
- Angular position
- Angular velocity

Derived measures:

- Isometric testing
 - Peak extensor torque (Nm/kg)
 - Peak flexor torque (Nm/kg)
- Isokinetic testing
 - Peak extensor torque at 60 deg/s (Nm/kg)
 - Peak flexor torque at 60 deg/s (Nm/kg)
 - Peak extensor torque at 120 deg/s (Nm/kg)
 - Peak flexor torque at 120 deg/s (Nm/kg)

In-lab Functional Assessments (only wrist and lumbar sensors will be worn during these tests):

- *Stair climbing test (SCT)*
 - Ascending and descending a flight of stairs (x2)
 - Will only be assessed during in-lab visits

- **6-minute walk test (6MWT)**
 - Distance covered in 6 minutes
 - Will only be assessed during in-lab visits
- **15-second step-up test:**
 - Number of step-ups in 15-second (4in step)
 - Will be assessed during both in-lab and at-home visits
- **7-meter gait test**
 - Get up from a chair, walk 7 meters, turn around, return to starting position, sit down
 - Will be assessed during both in-lab and at-home visits
- **Short Physical Performance Battery (SPPB).** SPPB includes the following tests
 - Balance tests (all performed with eyes open and under close supervision of a study staff member)
 - Side-by-side stand – standing with feet side-by-side for 10 seconds
 - Semi-tandem stand – standing with side of the heel of 1 foot touching the big toe of the other foot for 10 seconds
 - Tandem stand – standing with the heel of one foot in front of and touching the toes of the other foot for 10 seconds
 - Will only be assessed during in-lab visits
 - Gait speed test (x2)
 - walking over a 4-meter walkway
 - Will only be assessed during in-lab visits
 - Single chair stand
 - Will only be assessed during in-lab visits
 - Repeated chair stands i.e., 5 chair stands (x2)
 - Will only be assessed during both in-lab and at-home visits

Functional Assessment	Clinical Metric	Lumbar Sensor Measures	3-sensor inertial system
Stair Climb Test	Time to complete (sec)	NA	NA
15-second step-up test	Number of step-ups	NA	NA
6-minute walk test	Total distance traveled (meters)	Metrics will be calculated with in-house algorithms	Same metrics as lumbar sensor
7-meter gait test	NA	Metrics will be calculated with in-house algorithms	Same metrics as lumbar sensor
SPPB	Total balance test score Gait speed test score Chair stand test score Total score	Metrics will be calculated with in-house algorithms	Same metrics as lumbar sensor

6.1.2 In-Lab Pain Phenotype Assessments:

Quantitative Sensory Testing (QST) and Exercise-Induced Hypoalgesia (EIH)

Devices to be used: Medoc AS00301 AlgoMed Computerized Algometry System; von Frey monofilament set, Blood pressure cuff.

The QST is a valuable method for evaluating pain sensitization by examining the nociceptive response after application of different painful stimuli of controlled intensity to assess the function of both large and small nerve fibers and its central pathways.

Raw Data obtained:

- Pressure pain threshold (PPT): at the index knee joint and a wrist joint (in kgf)

Tasks to be performed:

- **PPT:** refers to the pressure at which the person first notes the pressure changing to slight pain. The pressure is applied using a hand-held algometer at the index knee and an uninvolving wrist (control site). PPT assessed at a site of disease (e.g., knee with OA) is a reflection of peripheral +/- central sensitization, whereas when it is assessed at an otherwise undiseased site (e.g., wrist as the referent site), it is a reflection of central sensitization. Three trials are performed at each site and the average of the last two trials is used in the analysis. Lower scores indicate greater “pressure pain sensitivity”. The outcome is the mean PPT (in kgf) across the three trials.
- **Temporal Summation (TS):** refers to the increased perception of pain from repetitive stimuli applied at a uniform interval. An exaggerated TS of pain characterizes many chronic pain conditions and is related to central sensitization. TS will be assessed by repeated pressure stimuli using a series of weighted monofilaments until a weight that evokes pain $\geq 4/10$ is reached. This weighted monofilament will then be applied 10 times at a rate of 1Hz. The participant’s response will be assessed immediately after the train of 10 stimuli, as well as 15 seconds and 30 seconds after completion on a numeric pain rating scale (from 0 to 10). TS will be considered to be facilitated if a positive value is obtained after the initial pain rating is subtracted from the greatest of the 3 post-stimuli pain ratings.
- **Conditioned Pain Modulation (CPM):** This test assesses the descending modulatory pathways, wherein the pain experienced by one noxious stimulus is diminished when a second conditioning noxious stimulus is applied. CPM will be assessed using the forearm ischemia test. The first PPT is obtained as described above. Then a blood pressure cuff is applied to the contralateral arm and inflated to above systolic. The participant then performs hand grips with a squeeze ball until the s/he rates their forearm pain as $\geq 4/10$, at which point a second PPT is obtained; if this is not achieved within 2 minutes, the second PPT is obtained. A ratio of the second PPT to the first PPT is an indication of CPM. A ratio that is $=<1$, indicating lack of increase in post-conditioning stimulus PPT will be defined as impaired CPM and a ratio >1 will be noted as normal CPM.
- **Exercise-Induced Hypoalgesia (EIH):** is a form of endogenous pain modulation and corresponds to the attenuation of pain following a single episode of exercise. EIH will be assessed as the change in PPT at the study knee before and after a quadriceps and hamstrings strength testing protocol. A reduction in PPT is considered a positive EIH.

Derived measures:

- PPT (kgf)
- Temporal summation (yes/no)
- CPM (yes/no)
- EIH (yes/no)

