7. ANALYSIS PLAN

7.1. Analysis of Primary Aim and Endpoints

Details of the analysis of this study will be documented in the Statistical Analysis Plan (SAP). The analyses described in the approved SAP will be followed if different from what is described in this protocol.

Primary Aim: Measure the effect of PT on functional performance using digital measures from wearable sensors.

The following analyses will be performed to address this primary aim.

A. Validate wearable sensor-based metrics of functional biomechanical tests in people with knee OA against optical motion capture

Data from the lumbar sensor and optical motion capture during gait and sit-to-stand tasks during in-lab visits will be used for this analysis. Wearable sensor metrics will be compared against gold standard metrics from the optical motion capture system using intra-class correlation coefficient (ICC) and its 95% lower and upper confidence limits. The ICC reflects both the degree of correlation and agreement between the measurements. We will interpret agreement between measurements according to the following benchmarks: $ICC \leq 0.4$ indicates 'poor', 0.4 to 0.59 'moderate', 0.6 to 0.74 'good', and 0.75 to 1 'excellent' reliability (Cicchetti et al., 1994). In addition, we will also compute the mean, variance and percentage error between the standard and the digital measurements. Bland–Altman plots and 95% limits of agreement (average difference ± 1.96 standard deviation of the difference) will also be computed.

B. Compare wearable sensor-based metrics of physical performance in people with knee OA with standardized physical performance outcomes.

Wearable sensors with excellent reliability from analysis A will be examined. Sensor-based metrics from lumbar sensor during physical performance tests in-lab will be correlated with standardized physical performance outcomes using Pearson's product-moment correlations or Spearman's rank order correlations depending on their normality.

C. Assess the effects of exercise-based PT on outcomes from wearable sensors during in-lab physical performance tests

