7.3. Analysis of Exploratory Aims and Endpoints

1. Assess whether sensor-based baseline measures can stratify treatment response

Wearable sensors with excellent reliability from analysis A in Aim 1 will be examined. Sensor data lumbar sensor during in-lab physical performance testing will be modeled as continuous exposure, as well as, tertiles. Multivariate logistic regression will be used to assess whether baseline wearable sensor metrics can predict treatment response while accounting for confounders such as age, sex, BMI, and baseline KOOS-derived WOMAC 3.0 pain score.

2. Assess whether participant phenotype; pain, physical performance, affective traits (catastrophizing), can stratify treatment response.

The following exposure definitions will be used.

- Pain phenotypes
 - Tertiles of PPT
 - Presence/absence of TS
 - Inadequate/adequate CPM
 - Inadequate/adequate EIH
 - Presence/absence of pain catastrophizing from pain catastrophizing questions
 - Presence/absence of widespread pain from joint homunculus
 - PainDETECT score (continuous)
- Physical performance
 - Tertiles of physical performance tests
 - Tertiles of strength tests

Multivariate logistic regression will be used to assess whether baseline exposure variables can predict treatment response while accounting for confounders such as age, sex, BMI, and baseline KOOS-derived WOMAC 3.0 pain score.

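### The only scoring rule for exercise-induced hypoalgesia runs opposite to the protocol's own definition, so literal coding would reverse the EIH result in Exploratory Aim 2

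*Protocol*

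**What the plan says.** Protocol 6.1.2 (In-Lab Pain Phenotype Assessments) describes PPT as the pressure at which a participant first feels slight pain. It gives the scale a direction: "Lower scores indicate greater" pressure pain sensitivity. It says that EIH "corresponds to the attenuation of pain following a single episode of exercise", measures it as the change in PPT at the study knee from before to after the quadriceps and hamstrings strength tests, and then scores it: "A reduction in PPT is considered a positive EIH".

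For conditioned pain modulation (CPM), which is also derived from two PPT readings, the section takes the ratio of the second to the first. A ratio of 1 or less is impaired, and "a ratio >1 will be noted as normal CPM".

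The analysis sections add labels only. Protocol 7.3 and SAP 4.4 both list the exposure as "Inadequate/adequate EIH", and SAP 3.3 lists EIH as a yes/no variable. Protocol 7.1 gives the SAP precedence: "The analyses described in the approved SAP will be followed if different from what is described in this protocol".

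**The concern.** The scoring sentence calls a fall in the pain threshold hypoalgesia. By the protocol's own account of PPT, a fall means that the knee has become more sensitive. The SAP cannot override the sentence because it contains no EIH rule of its own, so a programmer working from the documents has only this rule to apply. Nor does either document say whether 'positive' means 'yes' or 'adequate'.

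Exploratory Aim 2 enters baseline EIH in a logistic model for treatment response. Whether pain phenotype influences response to physical therapy is one of the four questions in Protocol 2.1. If the exposure is coded backwards, the report would say that participants whose pain threshold falls with exercise are the ones with adequate pain modulation, and any association with response would be read the wrong way round.

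**Working it through.** No figure in the documents depends on this rule, so there is none to reproduce. The check has three parts.

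**1. Direction, from Protocol 6.1.2**

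| Statement | Direction it implies |
|---|---|
| Lower PPT is greater sensitivity | A fall in PPT is more pain sensitivity |
| EIH is attenuation of pain after exercise | EIH is a rise in PPT |
| CPM: ratio above 1 is normal | A rise in PPT is the healthy response (parallel test) |
| EIH scoring sentence | EIH is a fall in PPT |

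The first two statements together contradict the fourth. The third concerns a different test, but it shows the direction used for the other PPT-based measure of pain modulation.

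**2. Effect of literal coding with no unchanged PPT values**

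Let x = 1 for a rise in PPT, with logit P(response) = b0 + b1·x + covariates. Literal coding uses x' = 1 − x. Substituting, logit P = (b0 + b1) − b1·x' + covariates. The coefficient changes sign, the odds ratio becomes 1/OR, and the covariate coefficients, model fit and p-value do not change.

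For assumed true odds ratios: 1/1.5 = 0.67, 1/2.5 = 0.40, 1/4.0 = 0.25.

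**3. Effect when some PPT changes are exactly zero**

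Unchanged participants are 'not positive' under both codings, so the inversion is no longer exact. Assumptions: 30% response among those whose PPT falls, unchanged participants respond like them, 60% of the remainder rise, and the true OR is 2.5.

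- Odds in the fall group: 0.30/0.70 = 0.4286. Odds in the rise group: 2.5 × 0.4286 = 1.0714, a response rate of 0.5172.
- 10% unchanged (rise 0.54, fall 0.36, zero 0.10). Response in zero plus rise = (0.10 × 0.30 + 0.54 × 0.5172)/0.64 = 0.4833, odds 0.935. Literal OR = 0.4286/0.935 = **0.46**.
- 20% unchanged (rise 0.48, fall 0.32, zero 0.20). Response in zero plus rise = (0.20 × 0.30 + 0.48 × 0.5172)/0.68 = 0.4534, odds 0.829. Literal OR = 0.4286/0.829 = **0.52**.
- Varying the rise share from 50% to 70% gives 0.45 to 0.47 at 10% unchanged and 0.50 to 0.53 at 20%.

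Number in the wrong group, taking 60 × 0.90 = 54 analysed (Protocol 4.2 attrition; all assumed to have a baseline EIH value): 54 with none unchanged, 54 × 0.90 ≈ 49 at 10%, and 54 × 0.80 ≈ 43 at 20%.

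Simulated adjusted fits (60 participants, 500 replicates, assumed true OR 2.5) agree. With none unchanged, the median OR was 2.70 with a rise coded as adequate and 0.37 with literal coding, and the sign reversed in every replicate. With 5%, 10% and 20% unchanged, the sign reversed in about 96%, 94% and 89% of replicates.

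**The case against.** The strongest reply is that this is a one-word slip. The name of the test, its definition and the CPM rule all show what was meant. Harm requires an analyst to follow the sentence against that context and also to equate 'positive' with 'adequate', which neither document states. Without unchanged values, the p-value and model fit are the same under either coding, so the answer to whether EIH is associated with response would not change; only its direction would. The odds ratios, tie rates and response rates above are assumptions.

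Much of this is fair, and it limits the weight of the point. The consequence is conditional, CPM is supporting analogy rather than a strict contradiction, and with ties a single sample will not always show the reversed sign. It does not remove the point. The sentence is the only scoring rule in either document, and for this exposure the direction is the finding. The unchanged fit and p-value also mean that, without ties, neither would reveal the error.

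One further objection stands: the documents do not say how zero change in EIH is classed. Calling it inadequate borrows the CPM convention, and the authors should confirm that choice.

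**Conclusion.** The concern holds. The EIH scoring sentence is wrong by the protocol's own definitions, and nothing in the SAP corrects it. If it is applied as written, with 'positive' read as 'adequate', the EIH odds ratio is inverted exactly when no PPT change is zero. When 10% to 20% are zero, it stays on the wrong side of 1 in expectation (0.46 to 0.52 for an assumed true value of 2.5). If the analyst instead codes a rise as adequate, the result is right despite the sentence.

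The reach is narrow: one of seven pain-phenotype exposures in an exploratory aim, with no effect on primary or secondary analyses or on the sample size. The error can be recovered from the raw PPT values. It should be corrected because the error is certain and the correction is small.

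**What to change.** State in Protocol 6.1.2, and repeat in SAP 4.4, that an increase in PPT at the study knee after the strength protocol (post minus pre greater than 0) is positive, meaning adequate, EIH, and that no change or a decrease is inadequate EIH. The authors should confirm the zero-change class and link the yes/no label in SAP 3.3 to the same rule. Settling this before analysis avoids a recode that would look post hoc.

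Separately, and at lower priority, Protocol 6.1.2 gives two PPT summaries. One sentence says: "Three trials are performed at each site and the average of the last two trials is used in the analysis". A later one makes the outcome the mean of all three. The two differ by (trial 1 − mean of trials 2 and 3)/3, so a first trial 0.6 kgf higher (assumed) shifts PPT by 0.2 kgf. A shift common to all participants would not move the PPT tertiles; unequal first-trial effects could. The authors should reconcile these to one rule and say whether it also governs the CPM readings and the PPTs before and after exercise.

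The cost is one sentence in each document for EIH and one for the PPT summary. No new data are needed, because knee PPT in kgf is already recorded.
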